Appendix 3: ICD codes to identify patients with comorbidities		
Code Type	Code or Code Range	Condition
ICD-9-CM DX	3310	Alzheimer's
ICD-10-CM DX	G30.x	Alzheimer's
ICD-9-CM DX	14.x- 209.x	Cancer
ICD-10-CM DX	C0.x-C96.x	Cancer
ICD-9-CM DX	43.x-44.39; 7854, V434	Cerebrovascular disease
ICD-10-CM DX	E08.x-E13.x; G45.x- 46.x; 60.x-I79.x; I96; Z9582.x	Cerebrovascular disease
ICD-9-PROC	3848	Cerebrovascular disease
ICD-10-PROC	04R.x-04RY4KZ	Cerebrovascular disease
ICD-9-CM DX	338.x	Chronic pain
ICD-10-CM DX	G89.x	Chronic pain
ICD-9-CM DX	428.x	Congestive heart failure
ICD-10-CM DX	I09.x-I13.x; I50.x; R57.x	Congestive heart failure
ICD-9-CM DX	49.x; 5064; 51.x; 7702	COPD/asthma
ICD-10-CM DX	J4.x- J479	COPD/asthma
ICD-9-CM DX	410.x-4149; 433.x	Coronary artery/heart disease
ICD-10-CM DX	I20.x-I259; 63.x-I6529; Z955; Z9861	Coronary artery/heart disease
ICD-9-CM DX	250.x	Diabetes
ICD-10-CM DX	E10.x; E11.x; E13.x	Diabetes
ICD-9-CM DX	345.x	Epilepsy
ICD-10-CM DX	G40.x-G40B19	Epilepsy
ICD-9-CM DX	00.x-129; 2515; 271.x-2892; 3064; 4474; 45.x; 53.x-57.x; 61.x; 75.x; 78.x; 893.x; 997.x	GI disorders
ICD-10-CM DX	A0.x; A2.x; A4.x; A5.x; B0x; B3.x; B6.x; B7.x-B8.x; E164; E73.x-E74.x; I85.x-1880; K2.x-K6.x; K9.x; N8.x; Q3.x-Q4.x; Q7.x; R10.x-R198	GI disorders
ICD-9-CM DX	V08, 042, 07953	HIV
ICD-10-CM DX	Z21, B20, B9735	HIV
ICD-9-CM DX	401.x-404.93	Hypertension
ICD-10-CM DX	I10.x-I132	Hypertension
ICD-9-CM DX	346.x	Migraine
ICD-10-CM DX	G430.x-G324B1	Migraine
ICD-9-CM DX	278.0x	Obesity
ICD-10-CM DX	E66.x	Obesity
ICD-9-CM DX	715.x; 7330.x	Osteoarthritis/osteoporosis
ICD-10-CM DX	M15.x-M19.x; M800.x; M81.x	Osteoarthritis/osteoporosis
ICD-9-CM DX	331.82-33.2x	Parkinson's disease
ICD-10-CM DX	G20.x-G3183	Parkinson's disease
ICD-9-CM DX	240.x-2469	Thyroid disease
ICD-10-CM DX	E00.x-E079	Thyroid disease

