8.2 Sample size and randomization

The primary outcome for this study is PHQ-9 utilization. Assuming 75% PHQ-9 utilization prior to implementation of the Pathway Platform and 90% PHQ-9 utilization after implementation of the Pathway Platform, we will need 100 patients per group, for a total of 200 patients, assuming 80% power and a 2-sided alpha of 0.05 using Pearson chi square test for two independent proportions. To allow for subgroup analyses the sample will include 200 patients per group, for a total of 400 patients; 200 patients will comprise the “post-implementation” cohort and 200 will comprise the “pre-implementation” cohort. **Table 2** presents additional sample size calculations based on different assumptions of PHQ-9 utilization.

Table 2: Sample size calculations based on different assumptions of PHQ-9 utilization, alpha = 0.05, Power = 80%.
--

PHQ-9 utilization pre-implementation	PHQ-9 in Pathway post-implementation	N patients per group
75%	80%	1,094 per group
75%	90%	100 per group
75%	95%	49 per group
50%	65%	170 per group
50%	80%	30 per group
50%	90%	20 per group

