8.3.3 Exploratory outcomes

Patient clinical and reported outcomes:

- The following patient reported outcomes will be collected in the Pathway Platform throughout the study. The difference in scores between the baseline measure, 6-months, and end of the study will be compared. This will be restricted to patients who completed these scales at these two-time points. To be inclusive of all patients, additional analyses will be conducted to compare first and last scores available:
 - PHQ-9
 - WHO-5
 - PDQ-D5

- The following patient reported outcomes will be collected in the Pathway Platform and described at 6-months and end of the study:
 - Antidepressant Medication adherence
 - Antidepressant Medication dose adjustment and switches
 - Side effects
 - Depression remission
 - Depression response
 - Goal attainment
- Patient reported outcomes (PAM-13, CollaboRATE and WSAS) will also be explored at 6 months and end of the study.

Pathway Platform and report utilization: Pathway Platform analytics will be explored to understand patient adherence to the platform which includes frequency of logging into the Pathway Platform and frequency of completing each of the Pathway Platform functionalities. Care-team utilization of Pathway Platform reports will also be explored, including describing type of care team members who viewed the Pathway Platform reports as well as frequency of viewing the reports.

Education utilization: Frequency of viewing material in the resource education center will be described by patient and by care-team members. Commonly viewed educational material will be highlighted.

Subgroup analysis: primary, secondary, and exploratory outcomes will be compared across a number of patient demographic and clinical characteristics, including PHQ-9 severity at baseline, comorbidities (see appendix 3 for comorbid conditions and ICD codes), app utilization by patients, and EMR report utilization by providers. Additional subgroup analysis will be conducted by type of care model at the site level (e.g. collaborative care vs. non collaborative care sites).

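### In Appendix 3 three ICD-10 comorbidity rows swallow another condition whole (cerebrovascular/diabetes, heart failure/hypertension, Parkinson's/Alzheimer's), so condition-specific subgroups under the three broader labels would be mislabelled

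*Combined protocol and SAP*

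**What the plan says.** Section 8.3.3 (Subgroup analysis) plans to compare the primary, secondary and exploratory outcomes across patient characteristics. One of these is "comorbidities (see appendix 3 for comorbid conditions and ICD codes"). Appendix 3 lists 17 named conditions with ICD-9 and ICD-10 codes and is the only definition given.

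The ICD-10 diagnosis rows that matter are:

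- Cerebrovascular disease: "E08.x-E13.x; G45.x- 46.x; 60.x-I79.x; I96; Z9582.x"
- Diabetes: "E10.x; E11.x; E13.x"
- Congestive heart failure: "I09.x-I13.x; I50.x; R57.x"
- Hypertension: I10.x-I132
- Parkinson's disease: G20.x-G3183
- Alzheimer's: G30.x

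Neither 8.3.3 nor Appendix 3 says what happens when one code falls under two conditions, or whether comorbidity is analysed by condition or as any versus none. On the sample size, section 8.2 states: "To allow for subgroup analyses the sample will include 200 patients per group".

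**The concern.** The appendix attaches two condition labels to the same codes. A patient whose only relevant code is a listed diabetes code meets the definition of diabetes and also that of cerebrovascular disease. The same happens with hypertension and heart failure, and with Alzheimer's and Parkinson's. A result reported for heart failure would then describe a group that includes everyone with a listed hypertension code, and a reader could not tell.

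The codes are the whole definition of the factor, so nothing later in the plan would correct the labels. Subgroup analyses in general are also the stated reason for taking 200 rather than 100 patients per group, although 8.2 does not single out comorbidity.

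**Working it through.** There is no planned figure to reproduce on this point. The nearby sample size of 100 per group (75% versus 90%, 80% power, two-sided 0.05) does reproduce with the pooled chi-square formula and is not in question.

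**Reading rule.** Drop the dots, treat .x as all sub-codes, and read a hyphen as a range. Row A fully contains row B if every entry of B lies inside some entry of A.

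**The three ICD-10 pairs**

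| Broader row | Range | Contained row | Entries | Inside |
|---|---|---|---|---|
| Cerebrovascular | E08 to E13 | Diabetes | E10, E11, E13 | 3 of 3 |
| Heart failure | I09 to I13 | Hypertension | I10 to I13.2 | 1 of 1 |
| Parkinson's | G20 to G31.83 | Alzheimer's | G30 | 1 of 1 |

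Among ICD-10-coded patients it follows that:

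- number flagged cerebrovascular ≥ number flagged diabetes
- number flagged heart failure ≥ number flagged hypertension
- number flagged Parkinson's ≥ number flagged Alzheimer's

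Nothing further can be said about numbers of patients without prevalences.

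**Screen of the other ICD-10 rows.** One of the 17 conditions has an unusable ICD-10 string as printed (migraine, G430.x-G324B1, which runs backwards). The other 16 give 16 × 15 / 2 = 120 pairs. The three full containments above are the only ones. There is one partial overlap: in the coronary row, "I20.x-I259; 63.x-I6529; Z955; Z9861", the entry 63.x-I6529 lies inside the cerebrovascular entry 60.x-I79.x if the missing letter in both is I (1 of 4 coronary entries).

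**Do the ICD-9 rows offer a clean standard?** For these three pairs they do not show the containment:

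- 250.x is not in the cerebrovascular row.
- 401.x-404.93 is not in 428.x.
- 3310 lies below the Parkinson's start of 331.82, though the end of that range is damaged.

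Elsewhere they overlap. Leaving out Parkinson's (331.82-33.2x) gives 120 pairs again. With short entries read as code prefixes:

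- Obesity 278.0x lies inside 271.x-2892 of the GI row, "00.x-129; 2515; 271.x-2892; 3064; 4474; 45.x; 53.x-57.x; 61.x; 75.x; 78.x; 893.x; 997.x": 1 of 1, a full containment.
- HIV 042 and 07953 lie inside 00.x-129 of the GI row: 2 of 3.
- 7854 in the cerebrovascular row, "43.x-44.39; 7854, V434", matches 78.x of the GI row: 1 of 3.
- Coronary 433.x lies inside 43.x-44.39 of the cerebrovascular row: 1 of 2.

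**The case against.** The strongest reply is about reach. The plan never commits to a cerebrovascular, heart-failure or Parkinson's subgroup. It names comorbidity as one exploratory factor among several, and an any-versus-none split would not be touched by these overlaps. Eligibility and the sample-size calculation do not use Appendix 3, and 8.2 speaks of subgroups in general. All of this stands, and it limits the point to a conditional one. It does not remove it: the appendix names 17 separate conditions, which suggests condition-level use, and a simple count of comorbidities would count these patients twice.

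The second reply is about the text. Some strings in the table have visibly lost characters, including two later entries in the cerebrovascular cell, and this may come from PDF reading. The printed ranges may also be shorthand for a longer source list. That is a good reason to check the source first. But the six strings behind the three containments are complete as printed, and none depends on a damaged entry.

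The third reply is that comorbidity flags need not be mutually exclusive. This is true, and partial overlap can be legitimate where a code denotes both conditions. Full containment is different, because one condition's codes alone then always trigger the other label.

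The ICD-9 counts are the weakest part. They depend on the prefix reading: read as plain numbers, 43.x-44.39 would not contain 433, while the cancer range 14.x- 209.x would overlap the GI range. They matter only if ICD-9-coded records are pulled, which the documents do not say. They support screening every row, and the main conclusion does not need them.

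**Conclusion.** The concern holds as printed. Three ICD-10 rows fully contain another listed condition, with no rule to separate them. A condition-level analysis run from Appendix 3 would put every ICD-10-coded diabetes, hypertension and Alzheimer's patient under cerebrovascular disease, heart failure and Parkinson's respectively.

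This rests on two assumptions: that the printed ranges are the ones used in the code pull, and that comorbidity is analysed by condition. The size in patients is unknown.

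The overall primary and secondary comparisons and the three contained subgroups are unaffected. The correction should be made before the subgroups are run, but it does not threaten the main result.

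**What to change.** 1. Check Appendix 3 against the source code list and restore any lost characters.
2. Replace E08.x-E13.x (cerebrovascular), I09.x-I13.x (heart failure) and G20.x-G3183 (Parkinson's) with only the sub-codes that denote the row's own condition, so that a diabetes, hypertension or Alzheimer's code alone does not set the other flag. Keep a sub-code in two rows only where it truly denotes both. The sub-codes have to come from the source list; these documents do not give them.
3. Screen the remaining rows in both code systems. If ICD-9 records are used, start with 278.0x, 042, 07953 and 7854 against the GI row, and 433.x against the cerebrovascular row. Do not take the ICD-9 rows as the general standard.
4. Add one sentence to 8.3.3 saying whether comorbidity is analysed by condition or as any versus none.

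A minor related point, again only if ICD-9 records are pulled: in Appendix 1 the bipolar entry 296.x also matches all 14 listed ICD-9 codes for major depressive disorder (seven under 296.2x and seven under 296.3x), so these should be separated from it.

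The cost is an appendix edit, one sentence and a re-run of the code pull. No patients or study procedures change.

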Appendix 4: OPTION-12 Questionnaire

1	The clinician draws attention to an identified problem as one that requires a decision making process.	Yes 1	No 0
2	The clinician states that there is more than one way to deal with the identified problem (' equipoise ').	Yes 1	No 0
3	The clinician assesses the patient's preferred approach to receiving information to assist decision making (e.g. discussion, reading printed material, assessing graphical data, using videotapes or other media).	Yes 1	No 0
4	The clinician lists 'options', which can include the choice of 'no action'.	Yes 1	No 0
5	The clinician explains the pros and cons of options to the patient (taking 'no action' is an option).	Yes 1	No 0
6	The clinician explores the patient's expectations (or ideas) about how the problem(s) are to be managed.	Yes 1	No 0
7	The clinician explores the patient's concerns (fears) about how problem(s) are to be managed.	Yes 1	No 0
8	The clinician checks that the patient has understood the information.	Yes 1	No 0
9	The clinician offers the patient explicit opportunities to ask questions during the decision making process.	Yes 1	No 0
10	The clinician elicits the patient's preferred level of involvement in decision-making.	Yes 1	No 0
11	The clinician indicates the need for a decision making (or deferring) stage.	Yes 1	No 0
12	The clinician indicates the need to review the decision (or deferment).	Yes 1	No 0
